## **Brief Overview**

We are proposing a 20-participant multi-group case series to examine the effects of the Neuro20 stimulation suit in the amputee and neurologic populations. Our primary aim is to examine the effects of the Neuro20 stimulation suit on walking outcomes. We hypothesize that the Neuro20 suit will improve gait kinematics, gait speed, and muscle performance. Our secondary aim is to examine the mechanisms of the neurologic response to training in the Neuro20 stimulation suit by examining the effects on autonomic function. The Neuro20 assessments and interventions will take place at the Brooks Rehabilitation Clinical Research Center. We propose interventions to include up to 12 sessions with the Neuro20 suit under direct supervision from study staff. Assessments will occur pre-intervention, mid-intervention, and post-intervention.

## **Section 1: Procedures**

## 1.1 Screening/Recruitment Procedures

Potential participants may be identified by healthcare staff who are part of their normal clinical care or research staff. Potential participants may also hear about the study by word of mouth or by witnessing exercise sessions with Neuro20 suit at Brooks Rehabilitation.

## 1.1.1 Inclusion/Exclusion Criteria

#### **Inclusion Criteria**

- At least one week post amputation or neurologic injury (i.e. brain injury, stroke, spinal cord injury) and deemed medically stable to participate in rehabilitation
- Able to provide Informed Consent by demonstrating the ability to follow a three step command

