#### **Exclusion Criteria**

- Pacemaker / Defibrillator or severe cardiac disease (Class IV according to New York Heart Association Functional Classification)
- Implanted medical devices
- Active DVT/thrombophlebitis
- Active Cancer
- Active fever, infection, or acute inflammation
- Pregnancy
- Epilepsy or uncontrolled seizures or seizure within the last 6 months
- Implanted stimulator or pump that cannot be turned off externally
- Significant, active wounds in areas stimulated by the suit
- Inability to follow a three-step motor command
- Bleeding tendency

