#### 1.2 Informed Consent Process

Informed consent will be obtained by approved study staff in a quiet area to allow for answering of all questions.

- Participant must be able to provide consent
  - Must give accurate yes/no responses
- This study does not allow consent to be provided by a legally authorized representative (LAR)

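### The protocol treats following a three-step command as proof of ability to consent, and describes no check that the person understands the study

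*Protocol*

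**What the plan says.** Three places in the Protocol bear on who may consent.

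- **1.1.1, Inclusion Criteria:** "Able to provide Informed Consent by demonstrating the ability to follow a three step command". Command-following is named as the way in which ability to consent is shown.
- **1.1.1, Exclusion Criteria:** "Inability to follow a three-step motor command". This mirrors the inclusion line but adds the word motor, which the inclusion line does not contain.
- **1.2, Informed Consent Process:** the participant must be able to consent, and beneath that requirement stands one specific test, "Must give accurate yes/no responses". The setting is also described: "Informed consent will be obtained by approved study staff in a quiet area to allow for answering of all questions". Consent through a legally authorized representative is not permitted.

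The first inclusion criterion admits people from one week after amputation or neurologic injury, and names brain injury, stroke and spinal cord injury as the neurologic diagnoses. They must be medically stable enough for rehabilitation.

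**The concern.** The protocol does not leave capacity open for staff to assess by their usual procedure. It fixes a test, and the test measures something else. Carrying out a three-step instruction shows attention, reception of language and execution. Giving accurate yes/no answers shows that simple questions are understood and answered reliably. Neither shows that the person has grasped what the study is for, what will be done, what may go wrong, who pays if it does, and that they may decline or stop.

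This matters most for candidates with brain injury or stroke soon after the event, in whom cognition or language may be impaired while simple commands are still obeyed. Because a representative cannot consent for them, entry depends on the judgement of the candidate's own capacity, and the written basis for that judgement is weak. What is at stake is whether consent from these participants is adequately informed. A secondary matter is that one criterion is asked to do two jobs: showing capacity, and showing readiness to take part in supervised exercise.

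**Working it through.** No arithmetic decides this point, and the protocol gives no figure to reproduce. The check sets what must be understood against what the written tests show.

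1. **What a participant agrees to.**
   - Sections 1.3 and 1.4 describe three assessments of at most four hours each (3 × 4 = 12 hours at most) and up to 12 sessions. The outlined session lasts 60 to 90 minutes, so 12 sessions would take 12 × 60 min = 12 hours to 12 × 90 min = 18 hours.
   - Section 2.1 lists soreness, skin irritation, tingling or burning, muscle contractions, and abnormal heart rate or blood pressure responses.
   - Section 2.1 also places the medical cost of an injury on the participant's insurance, with deductibles and co-payments.
   - Section 2.2 says that the alternative is not to take part, with no effect on care.

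2. **What each written test shows.**
   - Three-step command (1.1.1, inclusion and exclusion): the person can take in and carry out an instruction. It carries no content from item 1.
   - Accurate yes/no responses (1.2): the person answers simple questions reliably. The protocol does not say what the questions are about, so no content from item 1 is required here either.
   - Quiet area with questions answered (1.2): information is offered and queries are dealt with. This describes what staff provide, not what the candidate has understood.
   - General requirement of ability to consent (1.2): the right standard, but the only means given for showing it are the two tests above.

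3. **Can someone meet both specific tests without understanding?** Yes. A candidate with brain injury or stroke, medically stable one week after the event, who performs a three-step command and answers simple yes/no questions correctly, meets both. Nothing in item 2 requires this person to show knowledge of anything in item 1.

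4. **Is a check of understanding described elsewhere?** Reading the remaining sections, including Section 3 (monitoring and reporting) and Section 4 (oversight), none is found in the protocol text at hand.

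5. **Size.** The Brief Overview states "We are proposing a 20-participant multi-group case series", with no split by diagnosis and no rate of impaired capacity. The number of participants affected cannot be derived.

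**The case against.** The strongest reply has four parts.

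- **The requirements are cumulative.** A candidate must meet the inclusion line, avoid the exclusion and satisfy 1.2, where ability to consent stands as a requirement of its own and the yes/no line is not said to be sufficient. This stands in part: the sections do not contradict each other. It does not remove the gap, because adding the two tests together still shows no understanding.
- **There are other protections.** Approved staff obtain consent in a quiet setting, questions are answered, and an Institutional Review Board oversees the study. The bar on representatives also protects, since a person found unable to consent cannot be enrolled. This stands, and it would be wrong to say that nothing protects these participants. The bar does not help someone wrongly judged able.
- **The check may sit in the consent document.** Consent pages are not part of the text at hand, and Sections 2 and 3 of the Protocol read in places as if drawn from such a document. This stands, so absence can be claimed only for the protocol text. The inclusion line nevertheless states its own test of capacity and would need rewording even if the consent form contains a better one.
- **Teach-back is one option among several.** This stands. It is offered below as an example.

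A reader might infer stronger points that the documents do not support.

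- **That the rule wrongly excludes people with spinal cord injury.** The word motor appears only in the exclusion line, no movement is specified, so staff may use preserved movement, and ability to move bears on a study whose primary aim is walking.
- **That the rule fails in every neurologic group.** Eligibility of a diagnosis does not show failure in it.
- **That staff would reach different decisions on the same candidate.** Read together, the criteria give one answer: all must be met.
- **That data would be lost.** No passage says that data would be discarded if a consent were found wanting.

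**Conclusion.** The point holds in limited form. The inclusion criterion fixes command-following as the demonstration of ability to consent, 1.2 adds only accurate yes/no responses, and neither shows understanding of purpose, procedures, risks, costs or voluntariness. The concern is sharpest for brain injury and stroke from one week after injury.

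Its size cannot be given as a number of participants. It alters no estimate, sample size or analysis, and it does not invalidate the case series. It is a worthwhile correction to participant protection and to the clarity of an eligibility criterion.

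The conclusion rests on two assumptions. First, some people soon after brain injury or stroke can follow commands and answer yes/no questions without understanding the study; this is a general premise, and the documents give no frequency for it. Second, the protocol text at hand is what staff apply. If a consent document already requires a check of understanding, the remaining work is to make 1.1.1 and 1.2 refer to it.

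**What to change.** Separate the two purposes now joined in the inclusion criterion.

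1. **Inclusion Criteria (1.1.1):** require ability to give informed consent, shown by a brief check of understanding. One way is for the candidate to explain back the purpose, the procedures, the main risks, who bears the cost of care for an injury, and the right to withdraw, in any response mode so that speech or movement impairment does not decide the result.
2. **Section 1.2:** cite the same standard, so that the yes/no line does not stand as the only specific test there.
3. **Three-step command:** keep it only as a separate criterion for taking part in the training, with no reference to consent.

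The cost is rewording a few lines, a few extra minutes at the existing consent discussion, and possibly some candidates found unable to consent, who could not then enter because representatives may not consent for them. Design, sample size, intervention and analysis are unchanged.

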#### **Exclusion Criteria**

- Pacemaker / Defibrillator or severe cardiac disease (Class IV according to New York Heart Association Functional Classification)
- Implanted medical devices
- Active DVT/thrombophlebitis
- Active Cancer
- Active fever, infection, or acute inflammation
- Pregnancy
- Epilepsy or uncontrolled seizures or seizure within the last 6 months
- Implanted stimulator or pump that cannot be turned off externally
- Significant, active wounds in areas stimulated by the suit
- Inability to follow a three-step motor command
- Bleeding tendency

#### 1.2 Informed Consent Process

Informed consent will be obtained by approved study staff in a quiet area to allow for answering of all questions.

- Participant must be able to provide consent
  - Must give accurate yes/no responses
- This study does not allow consent to be provided by a legally authorized representative (LAR)

## 1.3 Assessments

Participants will complete pre-, mid-, and post-intervention assessments lasting no more than four hours each. Assessments may include any of the following:

Primary Aim Assessments (Gait and Muscle Performance)

- Gait kinematics
- Functional near-infrared spectroscopy during gait
- Clinical gait outcome measures
  - o 10-meter walk test
  - o Timed up-and-go
  - o 6-minute walk test
- Clinical measures of muscle performance
  - o 5-time sit-to-stand
  - Muscle strength testing
  - o Range of motion measurements

Secondary Aim Assessments (Autonomic Function)

- H reflex measurement
- Clinical spasticity assessments
- Pupillometry
- Heart rate variability

## Questionnaires

- Demographic information
- Injury and function classification
- EuroQoL 5D-5L (quality of life)
- Neuro-QoL (quality of life)
- Diagnosis specific participation scale

#### 1.4 Intervention

All interventions will occur at Brooks Rehabilitation. Each participant will complete up to 12 sessions (no more than 3x a week in frequency) under the direct supervision of study staff. We have outlined a potential 60 to 90-minute protocol utilizing several modes of the Neuro20 suit.

#### Modes:

- Strength this is to be primarily used with strength training exercises or task specific training.
- **Conditioning** this is to be primarily used to increase parasympathetic autonomic control and to condition the individual to Neuro20 stimulation.
- **Cool Down** this is to be primarily used at the end of sessions as an active recovery.
- Massage this is to be primarily used for muscle pumping and circulation.
- **Patterned Movements** this is to be primarily used for improved muscle performance within task specific training.

Operating Mode	Stimulation (Work) Period		Rest Period	
Strength	84 Hz	175 µs	No stimulation	No stimulation
Conditioning	40 Hz	175 µs	7 Hz	175 μs
Cool Down	100 Hz	75 µs	No stimulation	No stimulation
Massage	84 Hz	175 µs	7 Hz	175 μs
PEMS - Patterned Movements (all)	84 Hz	175 μs	No Stimulation	No Stimulation

#### **Protocol Example:**

- Conditioning: 20 minutes in supine to patient tolerance with monitoring of symptoms and vitals.
- Strength: 10 minutes of stimulation to abdominals, back extensors, and hip extensors while participant performs bridging in supine.
- Patterned Movements: 30 minutes of gait training with suit during task specific training.
- Cool Down 10 minutes in supine for active recovery.

#### Progression:

Because the sample population will be heterogeneous, the protocol will differ between participants. Stimulation time, intensity, and mode will be driven by the response to the intervention rather than a standardized progression. All will receive at least 20 minutes of conditioning as a warm up for at least the first session, strengthening and patterned movements as indicated, and a cool down. Progression will include less time in conditioning and more time in strengthening/patterned movement. Strengthening/patterned movement will be performed with task specific training. Fatigue, quality of movement, and patient symptoms will be monitored throughout and adjustments to stimulation time, intensity, and mode made accordingly.

## 1.5 Data Analysis

Data will be captured during pre-intervention, mid-intervention, and post-intervention assessments. Data will be compared against normative values when available and change scores from pre-, mid-, and post-testing will be calculated for absolute differences. Questionnaire data will be similarly analyzed except where individual responses cannot be summed as part of a total score such as in the Euro-QOL.

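### Does section 1.5 wrongly leave the EQ-5D-5L without an analysis of change because its responses cannot be summed?

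*Protocol*

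**What the plan says.** Section 1.5 of the protocol gives the general rule first: "Data will be compared against normative values when available and change scores from pre-, mid-, and post-testing will be calculated for absolute differences". The next sentence turns to questionnaires: "Questionnaire data will be similarly analyzed except where individual responses cannot be summed as part of a total score such as in the Euro-QOL". Nothing further is said there about the EuroQol instrument.

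The list under the Questionnaires heading, which follows section 1.3, includes the EuroQoL 5D-5L and the Neuro-QoL as quality-of-life measures, together with a participation scale specific to the diagnosis. Only the EuroQol is named as an example of the exception.

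The Brief Overview describes the design: "We are proposing a 20-participant multi-group case series". It also sets the order of aims: "Our primary aim is to examine the effects of the Neuro20 stimulation suit on walking outcomes". The secondary aim concerns autonomic function. Quality of life belongs to neither aim.

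**The concern.** Section 1.5 states only one analysis, and the EQ-5D-5L is the named example of data to which it is not applied in the usual way. The reason given is that the responses do not form a total. That a set of items has no total does not prevent a comparison between visits, because each ordered dimension can be compared within a participant. The protocol also appears to treat other multi-part data differently: section 1.3 lists "Range of motion measurements", which are several separate values with no stated total, and they fall under the change-score rule without any condition that they be summed.

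If the sentence did rule out an analysis of change, a patient-reported measure would be collected and then set aside for a poor reason. A later analysis plan that examined EQ-5D-5L change would contradict the protocol. If the plan stayed silent, the choice of summary could be made after the data were seen.

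**Working it through.** There is no figure in the protocol to reproduce on this point, so the check is a reading of the text, followed by a simple count.

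**1. What the exception covers.** The word of exception in section 1.5 qualifies the statement that questionnaires are analysed similarly. Two readings are possible:

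- Narrow: only the individual responses are excepted, and any overall score the instrument yields stays under the default.
- Wide: the whole instrument is handled differently from the default.

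On neither reading does the text say that the data are dropped or that change is not examined. Being analysed differently is not the same as not being analysed.

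**2. Whether the stated premise is right.** I take the name 5D-5L to mean five dimensions with five ordered levels each; this is an assumption, because the protocol does not spell it out. The dimensions describe different things and the levels are ordered categories. Not adding them into a raw total is correct, so the protocol states no error here.

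**3. Whether a dimension-level analysis would conflict with the protocol.** The default is that "change scores from pre-, mid-, and post-testing will be calculated for absolute differences", which means numerical subtraction between visits. The natural analysis of an ordered dimension classifies each participant as improved, unchanged or worse. That is an ordinal description and not an absolute difference.

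| Data | Natural comparison between visits | Fits the default of absolute differences? |
|---|---|---|
| Questionnaire with a total score | Difference in totals | Yes |
| Range of motion | Difference in each measurement | Yes |
| Ordered EQ-5D-5L dimension | Improved, unchanged or worse | No, so it needs different handling |

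The third row is where section 1.5 makes its exception. An analysis plan that reported the dimensions in this way would be consistent with the protocol.

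**4. Whether range of motion shows an inconsistency.** Each range-of-motion value is a numeric measurement, and its own difference has a meaning without any total. The condition about summing is attached to individual responses on questionnaires. Treating numeric measurements and ordinal responses differently is not a contradiction.

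**5. What the numbers can show.** Possible dimension comparisons per participant who completes the instrument:

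- pre to post only: 5 × 1 = 5
- pre to mid and pre to post: 5 × 2 = 10
- mid to post as well: 5 × 3 = 15

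How often the instrument is given is an assumption, because section 1.3 words the assessments as optional. These are counts of possible descriptions. They measure no bias, no loss of precision and no change in a conclusion.

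**6. What depends on it.** Section 1.5 describes comparison with norms and change scores only. It sets no hypothesis test and no significance level that a choice of EQ-5D-5L summary could distort. Neither aim uses the instrument.

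An argument from other scores that the instrument may provide, such as an index value or a visual analogue score, is left out here. The protocol mentions neither, so the argument would rest on knowledge from outside the document.

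**The case for a change.** The strongest case for the concern is that the protocol is not silent. It makes an explicit exception and attaches a reason to it. On the wide reading, the EuroQol is removed from the only analysis stated, including the comparison with norms, and lack of a total does not by itself justify that. An analysis plan that followed the wording closely might then omit EQ-5D-5L change altogether. In a small descriptive study the description of change is the result, so leaving it open matters more than it would beside a formal test.

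Part of this stands. The sentence is loosely worded, and it does not say which of the two readings is meant. It is also true that non-summable items can be compared between visits; had the protocol said that no such comparison would be made, its reason would not have supported the decision.

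The rest does not stand. The protocol does not say that, and the error appears only once an inference is added to its text. The worry about a choice made after the data are seen is the missing summary method in another form. Whether that method is fixed in advance cannot be judged without the analysis plan, and the scoring and tabulation of one questionnaire is commonly placed there. The fear that a sensible plan would have to contradict the protocol fails for the dimension-level analysis, as shown in step 3 above.

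**Conclusion.** The concern does not hold. Section 1.5 correctly declines to sum EQ-5D-5L responses and says that such data are not handled in the default way; it does not exclude them from an examination of change. What remains is an unstated method of summary for one questionnaire outside both aims, in a descriptive case series of 20 participants. That is not an error in the protocol. Following the text as written produces no wrong result for the walking or the autonomic aim.

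The conclusion rests on two assumptions: that the exception means different handling and not omission, which is all the words say, and that the instrument has five ordered dimensions, as its name indicates. It does not depend on what a statistical analysis plan contains, although a plan is the usual place for the remaining detail.

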## **Section 2: Risk Information**

## 2.1 Risks, Side Effects, and/or Discomforts

There are minimal risks to participating in this study. The participants may feel some muscle soreness consistent with exercise within the rehabilitation setting. They may also have minor skin irritation from using the device, which will be monitored. While using the Neuro20 suit, participants may experience tingling or burning sensations or muscle contractions in the muscles and skin under the pads. There is also risk of abnormal heart rate and blood pressure responses. Blood pressure and heart rate will be monitored every 20 minutes of stimulation and with any patient reports of cardiac related symptoms (lightheadedness, dizziness, headache, hot flashes, shortness of breath, etc.). All symptoms will be monitored by study staff and adjusted immediately to participant comfort.

As many individuals with neurologic injury demonstrate limitations in sensation, impaired sensation is not an exclusion criterion, but skin integrity will be closely monitored after each use.

While we believe the risk of injury during this study is minimal, please be advised that Brooks Rehabilitation will manage the participant's care consistent with the management of all treatment-related adverse events. The participant's insurance will be responsible for any medical cost including deductibles, co-insurance, or co-payments. Any injury requiring medical care will be reported to the Institutional Review Board providing oversight of this study.

